8.3 Secondary objectives

- To determine the functionality of the immune response to full and fractional doses at the 1-month post-boost time point using an opsonophagocytic assay.
- To compare vaccine efficacy against carriage of non-PCV10 serotypes 6A and 19A in the full dose PCV13 arms when compared to the fractional dose arms, using the full dose PCV10 2p+1 arm as a control, with primary analyses at 18 months of age and secondary analyses at 9 months of age. The carriage prevalence of the common vaccine serotypes (PCV10 serotypes) in the fractional dose arms will also be compared against the carriage prevalence in the full dose arms.
- To compare frequency and severity of local injection-site reactions and vaccine-related adverse events in the 28 days following immunization after fractional dose delivery and a full dose delivery.
- To determine the concentration of circulating IgG after the primary series of the 2p+1 schedule, prior to boost, at 9 months of age and after the boost at 18 months of age, estimate the duration of direct protection conferred by full and fractional dose schedules and use seroepidemiology to monitor acquisition rates.
- To compare carriage prevalence at 9 and 18 months of age and IgG concentrations at 4 weeks after the primary series after full dose of PCV10 in a 3p+0 schedule, and full/ fractional doses of PCV10/13 in a 2p+1 schedule.

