9.3.5 Randomisation & blinding

The infant will be randomised to one of the seven vaccine schedules and dosages by the study team at the clinic. At randomisation, half of the participants randomised to arms A-F (150 of every 300 in each arm) will be allocated to a sub-group with an additional blood draw at 9 and 18 months of age. This blood draw will be analysed to assess IgG persistence (Table 2a).

Infants will be randomised using pre-prepared sealed envelopes containing randomisation codes. Randomization codes will be prepared before recruitment starts by a person outside of the study. Allocations will be concealed until the envelope is opened by a member of the unblinded study team at each clinic during vaccine preparation. Participants will not be informed of the allocated vaccine and vaccine will be prepared by the unblinded team who will mask the barrel of the syringe to avoid observation of the volume. This will be important to avoid differential loss to follow up across the trial arms. Participants will be told that this is to avoid them becoming aware of the vaccination type before the end of the trial. Other than the vaccination team, other study personnel e.g. those observing reactogenicity and laboratory personnel will be blinded to the type of vaccine received by each participant. The study personnel preparing and administering the vaccine will not be blind to allocation in order to administer the vaccine, but will then not participate in safety assessments and will not reveal vaccination allocations to other trial personnel.

Blinding of the seventh, control, arm of vaccination with the full dose of 3p+0 schedule will be broken when participants return for their second visit at 10 weeks of age and those in the seventh arm (arm G) receive their 2nd PCV dose. This break in blinding is not expected to affect rates of withdrawal from the study or assessment of the study outcome measures. Participants in the other 6 arms will remain blinded as to full/fractional PCV10/PCV13 allocation and participants in the seventh arm will not contribute local injection site reaction data (See Table 2a and 2b: Time and events Schedule).

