11 LAB PROCEDURES

11.1 Blood sample management & testing

Venous blood samples will be collected at baseline (2ml), the D84 visit (approximately 18 weeks of age; 2ml) and, in trial arms A-F, at the 1-month post-boost visit (10-13 months of age; 2ml). Half of the participants enrolled onto trial arms A-F (150 in each arm) will have additional blood draws at 9 months and 18 months of age (2ml at each visit). A cumulative total of 4-10mls of blood will be collected from each participant by the end of the trial, depending on randomisation and allocation. The sample at baseline will be tested for anaemia in order to inform clinical care of the infant. All serum will be separated within 48 hours of sample collection and stored at -20 degrees Celsius at the KWTRP CGMR-Coast laboratories. All samples will be shipped to the UCL WHO Reference Laboratory for Pneumococcal Serology based at the Great Ormond Street Institute of Child Health. If any remaining volume is not shipped to UCL, samples will be stored at the KWTRP CGMR-Coast laboratories. Sample management will include monitoring of the number of freeze-thaw cycles experienced by each sample in a laboratory database.

At the UCL WHO Reference Laboratory for Pneumococcal Serology, sera will be assayed for antibodies to all vaccine-type capsular polysaccharides using the WHO reference ELISA following adsorption with cell wall polysaccharide and 22F polysaccharide at a concentration of 10 mcg/ ml (Details available at <http://www.vaccine.uab.edu/ELISA%20Protocol.pdf>). This assay is based on the original Wyeth assay used to generate the correlate of protection of 0.35 mcg/ml.

A subset of 50 sera from each of the trial arms A-F, at the 1 month post-boost time point will be used to estimate the functionality of the immune response to all vaccine serotypes using the multiplexed Opsono-Phagocytic Assay (MOPA; details available at <http://www.vaccine.uab.edu/UAB-MOPA.pdf>).

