IgG GMCs in a random selection of half the participants in trial arms A-F at 9 months of age (pre-boost) and at 18 months of age (9 months post-boost) will be used to 1) estimate the duration at which GMCs remain above the threshold for protection in the first 2 years of life after a 2p+1 schedule of full or fractional doses and 2) to monitor carriage acquisition rates.

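### The 9- and 18-month IgG persistence analysis in arms A-F names only GMCs of the sampled half and makes no use of the 18-week and 10-month titres measured in every infant of those arms

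*Combined protocol and SAP*

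**What the plan says.** Section 13.2 covers persistence in one sentence. It takes "IgG GMCs in a random selection of half the participants in trial arms A-F at 9 months of age" and at 18 months, and gives these GMCs two purposes: to estimate how long concentrations stay above the protective level in the first two years, and to follow carriage acquisition. It names no model, no pairing of visits and no role for other visits.

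The half is fixed in advance. Section 9.3.5 states that "half of the participants randomised to arms A-F (150 of every 300 in each arm) will be allocated to a sub-group" with the extra draws.

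The other samples are not restricted to that half. Section 11.1 schedules an 18-week draw for every participant and a further one "in trial arms A-F, at the 1-month post-boost visit (10-13 months of age; 2ml"). Table 2a shows the same schedule. At the reference laboratory "sera will be assayed for antibodies to all vaccine-type capsular polysaccharides", and no limit by visit is stated for arms A-F. Arm G has no 10-month sample, is assayed for seven serotypes at 18 weeks only (13.2), and is outside the persistence analysis.

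The secondary objective in 8.3 takes the post-primary concentration together with the 9- and 18-month concentrations, and sets out to "estimate the duration of direct protection conferred by full and fractional dose schedules". Section 13.3 leaves the detailed SAP to be finalised after the study starts and before database lock.

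**The concern.** In each of arms A-F, half the infants will have four post-vaccination titres (18 weeks, 9, 10 and 18 months) and the other half will have two (18 weeks and 10 months). The two late values of the second half are missing by design and completely at random. If titres correlate within infants, the 18-week and 10-month values of the unsampled half carry information about the arm means at 9 and 18 months. GMCs computed from the sampled half alone discard it.

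What is at stake is the width of the intervals around the 9- and 18-month GMCs, the fractional/full ratios at those ages, and the declines from 18 weeks to 9 months and from 10 to 18 months. These are the quantities available for describing duration under full and fractional doses.

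**Working it through.** **The plan's own figure.** There is none to reproduce: no sample size, power or precision is stated for IgG at 9 or 18 months.

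**Inputs**
- N = 300 per arm with 18-week and 10-month samples, n = 150 per arm with 9- and 18-month samples (9.3.5, 11.1).
- Loss to follow-up of 5% at 10 months (13.1), giving about 285 and 142. None is stated for 18 months.
- r, the within-infant correlation of log IgG between two visits: not in the documents, so assumed over a range. Equal variances at the visits are also assumed.

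**1. Level at 9 or 18 months, one other visit as predictor.** The regression estimator that uses all N infants has, relative to the half-sample GMC,

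variance ratio = 1 − r²(1 − n/N) = 1 − r²/2.

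CI width ratio is its square root, and effective n = 150 / variance ratio.

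| r | variance ratio | CI narrower by | effective n |
|---|---|---|---|
| 0 | 1.000 | 0% | 150 |
| 0.3 | 0.955 | 2.3% | 157 |
| 0.5 | 0.875 | 6.5% | 171 |
| 0.7 | 0.755 | 13.1% | 199 |
| 0.8 | 0.680 | 17.5% | 221 |

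A simulation with 20,000 runs gave 1.004, 0.960, 0.876, 0.761 and 0.682. The ceiling, when the other visits predict perfectly, is √0.5 = 0.707, or 29% narrower (effective n 300). With 285 and 142 infants the ratios move by no more than 0.001, and the effective sizes become 142, 149, 162, 188 and 209.

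**2. Same level, both the 18-week and 10-month titres as predictors.** With a common correlation r, R² = 2r²/(1 + r) = 0.333, 0.576 and 0.711 at r = 0.5, 0.7 and 0.8. The variance ratio 1 − R²/2 is then 0.833, 0.712 and 0.644. The one-predictor figures are therefore the cautious ones.

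**3. Decline from 10 to 18 months, compared with paired differences in the half.** In units of the variance of log IgG:
- paired differences: 2(1 − r)/n
- model: (1 − r²)/n + (1 − r)²/N
- ratio with n/N = 0.5: 0.75 + 0.25r

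At r = 0.5: 0.005833 / 0.006667 = 0.875. At r = 0.7: 0.003700 / 0.004000 = 0.925. At r = 0.8: 0.002533 / 0.002667 = 0.950. The variance falls by 12.5% to 5%, so the interval is about 6.5% to 2.5% narrower. Here the gain shrinks as r rises, because pairing already captures most of the correlation. With both full-sample visits and a common r the ratios are 0.833, 0.853 and 0.861.

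**4. On the GMC scale.** The only indirect source for an SD is the hoped-for post-boost precision of ±2 to 4 mcg/ml on GMCs of 13 to 35 (13.1). Pairing 2 with 13 and 4 with 35, and taking n = 300, both assumptions:
- ln SD = ln(1 + 2/13) × √300 / 1.96 = 1.26
- ln SD = ln(1 + 4/35) × √300 / 1.96 = 0.96

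If the same SD held at 9 and 18 months, the 95% CI of a 150-infant GMC would be ×/÷ exp(1.96 × SD / √150) = 1.17 to 1.22. Borrowing gives 1.16 to 1.21 at r = 0.5 and about 1.13 to 1.18 at r = 0.8. All 300 infants would give 1.12 to 1.15.

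**The case against.** Section 13.2 does not exclude a longitudinal model. It names GMCs and stops, 8.3 groups the post-primary, 9- and 18-month concentrations in one objective, and the detailed SAP is still to come. That the other titres will go unused is therefore an inference. This stands as a limit on the point but does not remove it: the text does state which quantity is to be used and in whom, nothing in 13.2 or 13.3 points to another, and the pending SAP is where a more precise estimator can be set beforehand.

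The gain may be small. It is nil for levels at r = 0, and natural boosting between visits could lower r. With intervals already near ×/÷ 1.2, no decision turns on it. This also stands.

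The model gives means at fixed visits. It does not by itself say how long titres stay above the threshold, nor address carriage acquisition. That is correct: it sharpens the inputs to the duration question, and the duration rule must still be written.

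Three stronger readings are tempting and are not supported:
- *That bleeding only half is wasteful.* It spares the other half two extra 2 ml draws, and Table 2a caps blood volume by weight. The point concerns the analysis only.
- *That half-sample GMCs are biased.* The half is drawn at randomisation, so they are not.
- *That the decline will be an all-infants 10-month GMC minus a half-sample 18-month GMC.* That comparison would show larger gains, but no section describes such a subtraction. Paired differences in the half are the fair comparator.

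**Conclusion.** The point holds as a cheap improvement. For arms A-F the plan reads persistence from unbiased half-sample GMCs and leaves available precision unused. For a 9- or 18-month GMC the interval would narrow by 0% to about 18% for r from 0 to 0.8 with one predictor. For the 10-to-18-month decline the variance would fall by 5% to 12.5% for r from 0.8 to 0.5, against paired differences.

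These sizes rest on an assumed r and, for the decline, on equal variances; the documents settle neither. For the unsampled half, missingness at random holds by design. Ordinary loss to follow-up does not share that guarantee. Persistence is a secondary estimation aim with no stated test, margin, power or precision target, so no stated conclusion or power figure changes. A reader should not infer that the persistence analysis is invalid or that more samples are needed.

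**What to change.** In 13.2 and the detailed SAP, specify one mixed model for repeated measures per product and serotype:
- outcome: log IgG at 18 weeks and 9, 10 and 18 months
- data: all infants in arms A-F with any of these titres, whether or not they are in the sampled half
- terms: arm-by-visit means, with an unstructured within-infant covariance
- outputs: arm GMCs at 9 and 18 months, fractional/full ratios at those visits, and the declines from 18 weeks to 9 months and from 10 to 18 months, each with a 95% CI

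Keep the half-sample GMCs as a descriptive table, and state separately how time above the threshold will be derived from the modelled means.

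The cost is a paragraph of SAP text and a standard model, with no extra blood, visits or assays. The small downside is reliance on roughly normal log IgG; the descriptive table offers a check on that.

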8.2 Primary objective

To determine whether fractional doses of PCV13/ PCV10 elicit non-inferior immunogenicity compared to full doses when delivered in a 2p+1 schedule with primary analyses at 4 weeks

after the booster dose (10 months of age) and secondary analyses at 4 weeks after the primary series (18 weeks of age). For the primary objective, immunogenicity will be assessed as the ratio of the geometric mean concentrations of IgG in the fractional/full dose arms. Secondary analyses will assess the proportion of infants achieving antibody levels above the threshold for protection (0.35 mcg IgG/ ml).

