13 STATISTICAL ANALYSES

13.1 Primary analyses and Sample size

The primary endpoint of non-inferiority will be reached if the lower CI around the ratio of geometric mean concentration (GMC) of IgG (fractional/full dose) is ≥ 0.5 (i.e. the 2-fold criterion) at 1-month post-boost dose (10 months of age).

A secondary endpoint will assess the proportion of ‘responders’, defined as those with serotype-specific IgG antibody concentration ≥ 0.35 mcg/ml[13] at 4 weeks after the primary series (18 weeks of age). Non-inferiority will be achieved if the lower limit of the 95% confidence interval (CI) around the difference in the proportion of ‘responders’ (fractional dose group – full dose group) is $> -10\%$ [76] post-primary series (18 weeks of age) for at least 8 of the 10 vaccine types in the PCV10 arms and at least 10 of the 13 vaccine types in the PCV13 arms. Assessments of non-inferiority will be made separately for each of the vaccine type serotypes. Our primary endpoint will be reached across all arms if non-inferior immunogenicity is achieved for the 10 serotypes in PCV10 as this is the standard of care in Kenya currently.

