The required sample size for the trial was calculated in order to ensure good power to detect both the primary and secondary immunogenicity endpoints, this approach is recommended in trials where both primary and secondary endpoints are important to determine the success of the intervention[77]. The proportion of children achieving the correlate of protection (IgG ≥ 0.35 $\mu\text{g/ml}$) varies across PCV10/13 serotypes after the primary vaccination series and by schedule (range 63.5-98.4%)[33, 76, 78-80]. In a prior study of PCV7 in Kilifi, the average proportion of children reaching the threshold antibody concentration across serotypes at 18 weeks of age was 87%[33]. The average proportion reaching the threshold antibody concentration at 18 weeks of age after 2 primary doses, 2 months apart, in European[81], Israeli[17, 82] and South African children[24] was also approximately 87% across 10 serotypes but serotype specific responses ranged between 63-97%. On this basis, to detect non-inferior immunogenicity (% responders) to 10 of the 13 serotypes in the PCV13 arms or 8 of the 10 serotypes in the PCV10 arms at 18 weeks of age with 90% power, we would need to enrol 300 infants per arm to declare non-inferiority using a margin of 10%, accounting for serotype-specific response rates, multiple serotype-specific comparisons and 5% loss to follow up at 4 weeks after the booster dose. Additionally, this sample size would allow us to perform an analysis on *all* vaccine types with a 12% non-inferiority margin with 84% power.

The 10-12% non-inferiority margin has been determined considering the public health consequences of a commensurate loss of protection, assuming 87% of infants achieve protection with the full dose.

There will be >99% power to declare non-inferiority using the criterion that the lower limit of the 95% CI for the ratio of GMCs (fractional/full dose) is >0.5. Based on the IgG GMCs elicited post boost in South Africa, which ranged between 13 and 35 mcg/ml for the PCV7 serotypes[24], we hope to be able to estimate GMCs with precision +/- 2-4 mcg/ml.

There will therefore be four pairwise comparisons of each vaccine type serotype for the primary endpoint of non-inferiority (i.e. full dose vs 20% dose; and full dose vs. 40% dose for each vaccine).

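### Duration of direct protection is read from how long the group GMC stays above 0.35 mcg/ml, which does not show what share of infants is still protected

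*Combined protocol and SAP*

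**What the plan says.** Section 8.3 sets a secondary objective to measure circulating IgG at 9 and 18 months and to "estimate the duration of direct protection conferred by full and fractional dose schedules". The only analysis text for it is the last paragraph of section 13.2. The data are "IgG GMCs in a random selection of half the participants in trial arms A-F at 9 months of age (pre-boost) and at 18 months", and the stated use is to "estimate the duration at which GMCs remain above the threshold for protection in the first 2 years of life". That paragraph does not repeat the threshold value; section 8.2 gives it as 0.35 mcg/ml.

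Other parts of the plan treat protection as something an individual infant has or lacks. Section 13.1 reads: "A secondary endpoint will assess the proportion of ‘responders’, defined as those with serotype-specific IgG antibody concentration" at or above 0.35 mcg/ml, assessed at 18 weeks. The same section sizes the trial "assuming 87% of infants achieve protection with the full dose", and explains the margin in those terms: "The 10-12% non-inferiority margin has been determined considering the public health consequences of a commensurate loss of protection".

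Section 8.2 also promises analyses of the proportion above threshold, but the time points it names are 18 weeks and 10 months. Nowhere is a proportion at or above 0.35 specified at 9 or 18 months. Section 13.3 defers detail to a later SAP, to be finalised before database lock; that SAP is not in the document reviewed.

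**The concern.** The threshold changes its unit between analyses. At 18 weeks it classifies infants; for persistence it is compared with a group mean. A group mean above the threshold says little about how many infants are above it, because that also depends on the spread of the antibody values.

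Section 5 says that data are lacking on how long protection lasts after a 2p+1 schedule in low- and middle-income countries, both before the booster and after it. The 9- and 18-month samples are the trial's contribution to that question. A statement that mean antibody stayed above threshold for some period could be read as a statement that the children were protected for that period, when a large minority, or even half, were not.

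**Working it through.** **Inputs.** Threshold 0.35 mcg/ml (section 8.2). Full-dose protected share 87% and margin 10-12 points (section 13.1). Persistence subset 150 per arm (section 9.3.5). Loss to follow-up 5% (section 13.1, stated for 4 weeks after the booster and carried to 18 months here as an assumption). The plan states no power or precision for the duration analysis, so there is no figure to reproduce.

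**Spread.** The log10 SD is not given. Section 13.1 hopes for a precision of 2-4 mcg/ml on GMCs of 13-35. If 2 is paired with 13 and 4 with 35, and each is read as a 95% half-width on the upper side with n = 285:

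- log10(15/13) x sqrt(285)/1.96 = 0.535
- log10(39/35) x sqrt(285)/1.96 = 0.405

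Using the lower side of the interval, or n = 300, stretches this to about 0.64. The pairing and the confidence level are my reading, and those GMCs are one month after the booster, not waned values. I therefore treat the SD as an assumption, with range 0.3-0.6.

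**Share below threshold at a given GMC.** If log IgG is normal, the share below 0.35 is 1 - Phi(log10(GMC/0.35)/SD).

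| GMC (mcg/ml) | SD 0.3 | SD 0.4 | SD 0.53 | SD 0.6 |
|---|---|---|---|---|
| 0.35 | 50% | 50% | 50% | 50% |
| 0.5 | 30% | 35% | 38% | 40% |
| 0.7 | 16% | 23% | 28% | 31% |
| 1.0 | 6% | 13% | 20% | 22% |

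The first row needs only symmetry of log IgG, and simulation of 1,000,000 draws at SD 0.3 and 0.6 confirmed it. Requiring the lower 95% limit of the GMC to clear 0.35 changes little. With n = 150 the share above at that point is Phi(1.96/sqrt(150)) = 56.4%, so about 44% are still below.

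**Two arms at one visit.** Suppose 87% of a full-dose arm is at or above 0.35 and the fractional arm has half its GMC with the same SD. The full-dose GMC is 0.35 x 10^(1.126 x SD). The fractional share is Phi(1.126 - 0.301/SD).

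| SD | Full GMC | Fractional GMC | Fractional share | Loss from 87% |
|---|---|---|---|---|
| 0.30 | 0.76 | 0.38 | 55% | 32 points |
| 0.40 | 0.99 | 0.49 | 65% | 22 points |
| 0.53 | 1.38 | 0.69 | 71% | 16 points |
| 0.60 | 1.66 | 0.83 | 73% | 14 points |

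Both GMCs exceed 0.35 in every row, while the loss exceeds the 10-12 point margin in every row.

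**Difference in duration when both curves reach the threshold.** With exponential decay and half-life h, an arm starting at GMC0 reaches a level c after h x log2(GMC0/c). The full-minus-fractional difference is h x log2(GMC_full/GMC_frac), in which c has cancelled. A rule based on the share of infants only changes c to 0.35 x 10^(SD x z), where z is the normal quantile of the required share. With a common SD and a common h the difference is the same: one half-life for a two-fold ratio.

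**Precision of a proportion.** 150 x 0.95 is about 142 per arm.

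- One arm at 87%: 1.96 x sqrt(0.87 x 0.13/142) = 5.5 points
- Difference at 87%: 1.96 x sqrt(2 x 0.87 x 0.13/142) = 7.8 points
- Difference at 50%: 1.96 x sqrt(2 x 0.25/142) = 11.6 points

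**The case against.** The sponsor could reply that this is a secondary, descriptive analysis with no pass mark. Section 5 itself takes pre-boost concentrations above 0.35 in South African infants as a sign that direct protection may have lasted, so reading persistence from concentrations fits the plan's own rationale. Individual values are collected, and the later SAP could report proportions anyway. Proportions at two ages are not a duration, and they may sit near a ceiling where GMCs discriminate better. Much of this stands. It is why the GMC summaries should stay, and why a duration measure is still needed. It does not make the GMC rule a measure of how many infants are protected. Section 5 also reports persistence as a proportion, with more than 75% of UK children above 0.35 for five of the seven PCV7 serotypes 2.5 years after vaccination.

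A reader might infer two stronger things that the documents do not support.

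- *That the rule conceals any fractional-versus-full difference in duration.* With equal SD and decay rate the choice of threshold cancels, as shown above. Concealment arises at a visit where both GMCs are still above 0.35, and the cancellation can fail if spread or decay differs between arms.
- *That duration is overstated by a known amount in every arm.* Against a target of 87% the GMC rule runs on for log2(0.76/0.35) = 1.1 to log2(1.66/0.35) = 2.2 extra half-lives at SD 0.3-0.6. But 87% is a planning figure for 18 weeks, not a definition of persisting protection. The plan gives no antibody half-life, so no error in months can be stated.

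**Conclusion.** The point holds as a mismatch between objective and measure. The objective asks how long children are directly protected, and the analysis reports how long a group mean exceeds a threshold that the plan otherwise applies child by child. About half of infants are below 0.35 when the GMC reaches it, and 30-40% when the GMC is 0.5. At a single visit the rule can treat arms alike when their protected shares differ by well over the margin.

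The 50% figure rests on approximate symmetry of log IgG; natural boosting could shift it. The other shares rest on log-normality and an assumed log10 SD of 0.3-0.6, and the two-arm example also on equal SDs. The primary endpoint, the GMC ratio one month after the booster, is not touched. The improvement is worth making because it costs almost nothing.

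**What to change.** In section 13.2 and in the SAP:

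1. Add, per serotype and arm, the proportion of infants at or above 0.35 mcg/ml at 9 and at 18 months, with the fractional-minus-full difference and its 95% CI. Present it as an estimate and not a non-inferiority test: the half-width of a difference is about 7.8 points at 87% and 11.6 points at 50%, too wide for a 10-12 point margin to be tested reliably.
2. Define duration as the time for which the proportion at or above 0.35 stays above a level stated in advance, derived from the individual IgG values. Arms A-F are also bled at 18 weeks and 10 months (Table 2a), so each waning interval has a start and an end. Mark any crossing later than 18 months as extrapolation, since no sample is taken after that age.
3. Keep the GMCs at each time point alongside.

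The cost is a few lines of SAP wording and some extra tables. No visits, samples or assays change. The level should be fixed before the persistence data are seen.
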